The importance of protein in nutrition is momentous to one's health. Dietary proteins are essentially nutritional because of their constituent amino acids, which the body uses to synthesize its own proteins, as well as nitrogen-containing molecules that are essential for life (1). The Recommended Dietary Allowance (RDA) for daily protein intake in healthy adults is $0.8 \text{ g}\cdot\text{kgBW}^{-1}\cdot\text{day}^{-1}$ (2). Younger individuals who participate in recreational or competitive activities, however, often attempt to go beyond the RDA by using protein supplements to help increase performance. For example, Coburn et al. (2006) demonstrated that protein supplementation in conjunction with an eight-week resistance-training program elicited greater improvements in muscle hypertrophy and strength when compared to carbohydrate supplementation in untrained men. There were 3.2 to 17.5% increases in muscle cross-sectional area of the quadriceps femoris musculature and 14.5 to 30.3% strength gains in the leg extensors (3). Furthermore, several expert groups have recently advocated that certain individuals, such as older persons, should increase their daily intake range (1.0 to $1.5 \text{ g}\cdot\text{kgBW}^{-1}\cdot\text{day}^{-1}$) to support the preservation of muscle and function (4-6). Other conditions also place greater than normal demands on amino acids, such as hypercatabolic stressed states, like that experienced by burn patients who's muscle protein breakdown rate increases by impairment to inward transmembrane transport of circulating blood amino acids (7, 8). Deutz et al. (2011) found that an experimental enriched protein "medical food" comprised of 27% of calories as total protein resulted in postprandial increases in MPS rates for 5 hours by ~33% ($0.073 \pm 0.023\% \cdot \text{h}^{-1}$ to $0.097 \pm 0.033\% \cdot \text{h}^{-1}$) in advanced cancer patients. Thus, continually reassessing new and innovative nutrient therapies is necessary for extending the findings of existing studies after technological advances, and for providing nutritional support-to-support health. Therefore, we have developed a leucine-enriched protein bar that contains an effective dose of leucine in a high-quality protein matrix consisting of bovine milk proteins. Of all of the essential amino acids, leucine appears to be the most potent in activating anabolic signaling (16, 17, 19). The product weighs about 40g per serve, is low in energy (~180 kcal per serve), palatable, and does not interfere with appetite or subsequent meal intake.

It is well known that dietary protein is a powerful transient stimulator of the muscle protein synthetic rate (MPS) (9-11) whereby changes in MPS in response to feeding may be regulated by specific downstream target proteins of mammalian target of rapamycin signaling, such as S6K1, rpS6, and eIF2B (11). A meal deficient in protein, however, does not increase the rate of MPS because a rise in the bioavailability of amino acids does not occur (12, 13). In addition, the source of dietary proteins has been shown to impact postprandial blood levels of amino acids. The concept that certain types of proteins are "fast acting" or "slow acting" has been shown to affect the postprandial profile of amino acids appearing in the systemic circulation (13). Native whey and micellar casein are both dairy proteins that contain a similar amount of essential (EAA), but blood EAA levels increase faster and to a higher level after the consumption of whey protein (13, 14). Differences in gastric emptying, digestion and absorption kinetics between micellar casein and native whey are the underlying factors (13). Nonetheless, micellar casein protein has been shown to protract MPS in humans (15). Despite the significant amount of information gained with respect to both of these protein sources, the effects of combinatorial

Supplementation of a Leucine-Enriched Dairy Protein Blend: Chronic and acute metabolic responses in young men and women

formulations on the postprandial profile of amino acids appearing in the blood is less well known.

Purpose and hypothesis

The primary purpose of this study is to evaluate changes in integrated (day-to-day) rates of myofibrillar MPS in response to the product and a short-term resistance training program in young men and women. A secondary purpose is to assess the acute postprandial skeletal muscle protein signalling response to the ingestion of the product in young men and women. Based on the results of a previous dairy protein bioavailability study (13) and our previous results (17, 18) we hypothesize that training + supplementation will result in greater integrated rate of muscle growth.

Experimental approach

In a cross-over, randomized controlled trial, 10 healthy young participants (5 men and 5 women) will be recruited to undergo exercise resistance training randomized to habitual diet or habitual diet and supplementation (2 x per training session). For two of the training sessions we will utilize a uni-lateral resistance exercise model to identify the acute effects of exercise and exercise + supplementation on the integrated rate of myofibrillar MPS within subject. This model enhances statistical power and eliminates between-subject differences impacting our outcomes. Throughout the study participants will record their macronutrient dietary intake. In addition, baseline body composition will be assessed with dual-energy x-ray absorptiometry.

Sample size estimate. We have previously detected significant alterations in myofibrillar fractional synthetic rates and lean muscle mass in response to step-reduction, and following the consumption of dietary protein and energy restriction (18-22). As a proof-of-concept investigation we will recruit $n=10$ per group.

METHODS

Body composition will be determined using dual energy x-ray absorptiometry (DXA) scans. The DXA procedures use a small amount of radiation to determine the bodies fat, bone, and lean mass. The procedure takes approximately seven minutes and involves lying still on an open bed while the sensor passes over the body.

Integrated rates of protein synthesis will be assessed with the precursor-product method using ingested deuterium labeled water (70 %D₂O) as we have shown previously (23, 24). Briefly, to increase deuterium (²H) enrichments in total body water to ~1%, participants will consume 4 D₂O doses (0.8ml/kg lean body mass per dose) on the loading day and 1 dose (0.8ml/kg lean body mass) on maintenance days. Total body water ²H enrichment will serve as a surrogate for plasma alanine ²H labeling (24-26). Daily saliva sampling will be continued until the end of the experimental trial to assess precursor pool enrichments. Muscle samples (~40–50mg) will be separated into myofibrillar and sarcoplasmic fractions and processed as previously described (27)

Supplementation of a Leucine-Enriched Dairy Protein Blend: Chronic and acute metabolic responses in young men and women

for analysis by gas chromatography combustion isotope ratio mass spectrometry (Metabolic Solutions, Nashua, NH). Briefly, muscle preparations will be analyzed for deuterated-alanine (^2H -alanine) with a Thermo Finnigan Delta V isotope ratio mass spectrometry coupled to a Thermo Trace GC Ultra with a gas chromatography combustion interface III and Conflow IV. Saliva samples will be analyzed for ^2H enrichment by cavity ring-down spectroscopy using a Liquid Water Isotope Analyzer with automated injection system.

Saliva Sample Instructions

A saliva sample will be taken every day during the study. The participant will use a labeled sampling tube corresponding to the specific day of the study and calendar date.

1. Saliva sample taken right before, or at least 30 minutes after, eating or drinking anything, including the heavy water (D₂O). The best time to take it is first thing in the morning after waking up and before having breakfast.
2. Open the top lid of the plastic salivette vial by popping the lid off sideways.
3. Remove the white, cotton swab from inside the vial. Cotton swab is placed in the mouth.
4. Gently chew and suck on the cotton swab for about 60 seconds, until the swab is completely saturated with saliva (or until the participant can no longer prevent themselves from swallowing the saliva produced).
5. Place the wet swab back inside the salivette vial and replace the cap, making sure it's securely on.
6. Do not spit into the plastic salivette vial at any time.
7. Place the salivette vial back inside the plastic Ziplock bag provided.
8. Place the Ziplock bag with the used salivette(s) inside a freezer.
9. Keep the Ziplock bag in a freezer until your next study appointment.

Please keep all unused salivettes stored at room temperature. Do not store unused salivettes in the freezer as these will be difficult to saturate. One Ziplock bag is for unused salivettes, the other Ziplock bag is for used salivettes (in the freezer).

Supplementation of a Leucine-Enriched Dairy Protein Blend: Chronic and acute metabolic responses in young men and women

[figure not shown]
Muscle biopsies will be sampled from the *vastus lateralis* using the Bergstrom technique before and after resistance training with either supplementation or habitual diet. Biopsies will be analysed for markers of protein synthesis utilizing Western blotting and PCR in addition to integrated MPS. The molecular mechanisms that underpin MPS in response to stimulation are complex, multifactorial and remain largely unknown. However, what is known is that proteins contained within the Akt-mTORC1-p70S6K1 signaling axis appear key. Thus, we propose to examine how the content of proteins contained within the Akt-mTORC1-p70S6K1 signaling axis change during our intervention. We also will examine changes in the DNA-protein ratio (an indicator of cell size) as well as mRNA expression of myogenin, MAFBx and MuRF1, some of which have been shown to change in response to muscle growth, using real-time PCR. ***Thus, our molecular analysis coupled with the use of the deuterated water methodology provides a mechanism-based clinical approach to study the impact of supplementation on skeletal muscle health.***

Venous Blood Sampling

A needle will be inserted into a forearm vein by a physician or a medically trained and certified member of the laboratory group, and a blood sample will be drawn (~5 mL or 1 teaspoons). The discomfort of this procedure is transient and is very similar to having an injection by a needle, e.g. when donating blood. Upon removal of the needle any discomfort should subside. During the course of the experiment, five blood draws will occur. In this experiment, the total blood taken is ~50 mL, which is 1/10th of the blood removed during a donation to a blood bank. This amount of blood loss is not enough to affect your physical performance in any way. After each blood sample has been taken pressure will be placed on the site in order to minimize bleeding and facilitate healing. The insertion of a needle for blood sampling is a common medical practice and involves few risks if proper precautions are taken. The needles are inserted under completely sterile conditions; however, there is a theoretical risk of infection. There is a chance of internal bleeding if adequate pressure is not maintained upon removal of the needle. This may cause some minor discomfort and could result in bruising/skin discoloration, which could last up to a few weeks. In very rare occasions, trauma to the vessel wall could result in the formation of a small blood clot, which could travel through the bloodstream and become lodged in a smaller vessel. However, we have never experienced such a complication after several thousand blood draws.

Resistance training will be composed of CrossFit style exercises individually customized to each participant (28). Prior to trial initiation, participants will report to the laboratory for familiarization of these types of exercises. In addition, for uni-lateral lower body resistance training sessions participants will perform 3 sets of leg press and leg extension exercises to volitional failure. 3-5 repetition maximum testing will be performed during the familiarization session to estimate 1-RM values for the leg press and leg extension exercises to allow for the determination of loads equal to approximately 80-90% 1-RM. For each exercise 6-10 repetitions/set will be completed.

Supplementation of a Leucine-Enriched Dairy Protein Blend: Chronic and acute metabolic responses in young men and women

Schematic overview of study design. DXA, dual-energy X-ray absorptiometry.

Statistics

Two-way repeated measures ANOVAs with time and treatment as factors will be used to compare differences between supplementation + exercise and habitual diet over the 8 days of resistance training. Where significant interaction is detected, post-hoc test will be applied to locate these differences. Statistical significance is set at $P < 0.05$. Calculations and analyses will be performed using the Prism V.7. and SPSS V.25. software packages.

Knowledge translation

The primary form of knowledge translation from these projects will be via conference presentations, published scientific papers, and press releases. We anticipate at least one major paper to arise from the project described here and at least that number of presentations at National and International meetings from Drs. [name] and [name]. We have a good publication record and would also opt for an online/open access journal or opt to pay an open access fee to allow wider use of our data. In addition, the PI gives at least 1-2 keynote lectures at various conferences both at National and International meetings. Hence, there will be relatively widespread dissemination of the data from these trials. As an adjunct member in the Department of Medicine, Faculty of Health Sciences, the PI is also positioned to present this work via Grand Rounds and other local seminars to clinicians to get information to those who can implement the findings into their practice. There will also be press releases that accompany each manuscript to more widely publicize the findings and garner the interests of clinically-oriented web services such as Web MD, Medscape, The Doctor's Page, and Healthcentral.com. We will also work with the McMaster Knowledge Translational Team, <http://www.mcmaster.ca/cfh/knowledgetranslation.html> - using McMaster PLUS, which is a premium 'literature service' at McMaster University designed to decrease the 'noise-to-signal

Supplementation of a Leucine-Enriched Dairy Protein Blend: Chronic and acute metabolic responses in young men and women

ratio' in articles from clinical journals. This service sends registered physicians e-mail updates with links to articles that are relevant to their discipline.

References

1. Grooper SS, Smith JL (2012). *Advanced Nutrition and Human Metabolism*. Belmont, CA USA: Wadsworth, Cengage Learning

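### The secondary purpose is an acute postprandial signalling response, but the signalling endpoint the text defines is protein content across the intervention, and the one stated analysis covers the 8 training days

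*Combined protocol and SAP*

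**What the plan says.** **Aim.** Purpose and hypothesis gives as the secondary purpose to "assess the acute postprandial skeletal muscle protein signalling response to the ingestion of the product". The hypothesis that follows concerns the integrated rate of muscle growth. None is given for signalling.

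**Sampling.** The Methods paragraph on muscle biopsies places the vastus lateralis samples "before and after resistance training with either supplementation or habitual diet". The readable text gives no interval between ingestion and biopsy. A schematic of the design is captioned but does not appear in the text available for review.

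**Endpoint.** The same paragraph opens broadly: "Biopsies will be analysed for markers of protein synthesis utilizing Western blotting and PCR in addition to integrated MPS". It then says what the signalling work will be: "we propose to examine how the content of proteins contained within the Akt-mTORC1-p70S6K1 signaling axis change during our intervention". It adds the DNA-protein ratio "as well as mRNA expression of myogenin, MAFBx and MuRF1". Phosphorylation is not named in any of this.

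**Analysis.** Statistics gives a two-way repeated measures ANOVA with time and treatment as factors, comparing supplementation plus exercise with habitual diet "over the 8 days of resistance training", at a significance level of 0.05. No separate analysis of an acute response is described.

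**The concern.** An acute postprandial signalling response is a short-lived change in the activation state of pathway proteins after a feed. The protocol's own background treats it that way: it describes leucine as a potent activator of anabolic signalling and the effect of dietary protein on synthesis as transient. The total amount of a pathway protein is a different quantity. It can stay flat while the pathway is switched on, and it can drift over days of training for reasons unrelated to a single feed.

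Two things are at stake.

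- If the laboratory follows the defined endpoint, the trial reports protein abundance over the intervention. That neither shows nor excludes an acute response to the product, and a flat result could be read as no signalling effect.
- If the laboratory measures phosphorylation anyway under the broad Western blot wording, the marker, the time point and the contrast are all chosen after the fact, in a study of 10 participants.

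**Working it through.** No stated figure bears on this point, so the check sets the aim against what the text defines, element by element.

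| Element | What the aim needs | What the text gives | Where |
|---|---|---|---|
| Measurand | Activation of signalling proteins | Content of Akt-mTORC1-p70S6K1 proteins; also unspecified Western blot and PCR markers, DNA-protein ratio and three mRNAs | Methods, muscle biopsies |
| Anchor in time | Ingestion of the product | Resistance training; interval from ingestion not in the readable text, possibly in the schematic | Methods, muscle biopsies; schematic caption |
| Analysis | A contrast at a post-ingestion time | Time-by-treatment ANOVA over the 8 training days; levels of time not listed | Statistics |
| Acute design element | Linked to signalling | Two unilateral sessions, with integrated myofibrillar synthesis as their stated outcome | Experimental approach |

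1. *Measurand.* Content is the one signalling quantity the text defines. The general sentence on markers does not rule out phospho-proteins, but a general phrase is not a prespecified activation endpoint. The DNA-protein ratio and the three mRNAs are not measures of Akt-mTORC1-p70S6K1 activation either.
2. *Timing.* This row is open. The sampling phrase could mean around a single session or around the whole training block. Experimental approach gives the supplement twice per training session, so a biopsy after a supplemented session could be postprandial.
3. *Analysis.* A biopsy near a session could be a level of the time factor, but no text says so and no acute contrast is defined.
4. *Combination.* Suppose the schematic does show a biopsy soon after ingestion. Content measured at that biopsy would still be abundance, so the measurand gap remains.

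*Context on precision.* The plan gives no effect size, SD or power for its 10 participants. Take a paired contrast with n = 10 and two-sided alpha 0.05 (the sidedness is an assumption). The normal formula for the detectable difference, in SDs of the within-participant difference, is (z for alpha + z for power) / √n:

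- 80% power: (1.96 + 0.84) / √10 = 0.89 SD
- 90% power: (1.96 + 1.28) / √10 = 1.03 SD

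The noncentral t, which is the better guide at this size, gives 1.00 SD and 1.15 SD. A paired activation contrast would thus have 80% power only for a difference of about one SD. The point itself does not rest on these numbers.

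**The case against.** The strongest reply is that the plan is under-specified, not wrong. Western blotting is planned in general terms, and a laboratory studying this pathway may well probe phospho-targets. The sampling phrase can be read as around a session. The two unilateral sessions are described as acute, with supplementation at each training session. Biopsy and feeding times would naturally sit in the schematic, and its absence here is not a fault of the plan. The ANOVA does not list its time levels, so the 8 days need not mean a single start-to-end contrast.

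Most of this stands, and it limits the point. Three stronger inferences are tempting and should not be drawn:

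- *That protein content is all that will be measured.* The biopsy paragraph lists other assays and leaves the Western blot targets open.
- *That the secondary purpose is beyond answer.* With an ingestion-linked biopsy and phospho-targets it could be addressed, and the documents exclude neither.
- *That the mismatch can be sized by setting the five-hour feeding window in the background against the length of training.* Those five hours describe a muscle protein synthesis rate in advanced cancer patients given another product. A biopsy is also a point sample, and the supplement is given repeatedly.

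The reply does not remove the explicit definition of the signalling work as change in content during the intervention, or the lack of any stated acute contrast. The schematic could settle timing; it would not turn content into activation.

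**Conclusion.** The point holds as a mismatch between the secondary purpose and the endpoint and analysis the text defines for it. Following the stated measurand would not answer the acute question, whatever the biopsy times turn out to be. Whether the sampling schedule could support that question is unknown from the readable text.

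The effect is confined to the secondary purpose, all of which is affected. The primary comparison of integrated myofibrillar synthesis is not touched. The change is worth making before samples are analysed, with medium confidence. The conclusion assumes that signalling response means activation, as the protocol's background suggests, and that no other document prespecifies phospho-targets.

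**What to change.** Amend the biopsy paragraph and Statistics as follows.

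1. **Endpoint.** On the Western blots already planned, measure phosphorylated as well as total Akt, mTOR and p70S6K1. Make activation the signalling outcome, for example phosphorylated relative to total protein. Content can stay as a separate, descriptive outcome.
2. **Timing.** State which scheduled biopsy follows ingestion and by how long, citing the schematic if it already shows this. State whether a pre-ingestion reference exists.
3. **Analysis.** Specify a paired, within-participant contrast of supplement versus habitual diet at that biopsy, as change from the pre-ingestion reference where there is one, and separate from the 8-day ANOVA. Without a reference, say that the contrast assumes comparable pre-ingestion levels in the two conditions.
4. **Fallback.** If no scheduled biopsy lies in the postprandial period, restate the secondary purpose as change in content of Akt-mTORC1-p70S6K1 proteins over the training period, and make no acute postprandial claim.

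*Cost.* Protocol and SAP wording, extra antibodies, and some lysate. The lysate matters: the muscle samples are about 40–50 mg and also feed the synthesis measurement, so the laboratory should confirm there is enough. Under the fallback, the price is a narrower secondary claim.

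### The stated D2O doses give about 0.3% body-water enrichment after loading, and about 0.5–0.8% by day 8, against a stated ~1%; saliva may also be sampled on either side of the daily dose

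*Combined protocol and SAP*

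**What the plan says.** The Methods paragraph on integrated protein synthesis uses 70% D2O. It gives the aim and the start of the schedule in one sentence: "enrichments in total body water to ~1%, participants will consume 4". The sentence continues with the doses: "doses (0.8ml/kg lean body mass per dose) on the loading day and 1 dose (0.8ml/kg lean body mass) on maintenance days". Body-water enrichment then stands in for plasma alanine labelling, and it is measured daily: "Daily saliva sampling will be continued until the end of the experimental trial to assess precursor pool enrichments". The saliva assay is named ("enrichment by cavity ring-down spectroscopy using a Liquid Water Isotope Analyzer with automated injection system"), but no assay precision is given.

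Saliva Sample Instructions, step 1, sets the timing: "Saliva sample taken right before, or at least 30 minutes after, eating or drinking anything, including the heavy water". It adds, as advice only: "The best time to take it is first thing in the morning after waking up and before having breakfast". The readable text gives no clock time for the D2O dose and no fixed order of dose and sample.

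The outcome at stake is the main one: "The primary purpose of this study is to evaluate changes in integrated (day-to-day) rates of myofibrillar MPS in response to the product". The only duration in the readable text is in Statistics: "over the 8 days of resistance training". That is the length of training. The number of labelling days may be in the design schematic, which is not shown.

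**The concern.** Body-water enrichment is the denominator of the synthesis rate. At a given synthesis rate, the label that muscle gains is proportional to the average precursor level over the labelling window. If the stated doses deliver well under 1% over that window, the muscle signal is smaller than a reader of the protocol would plan for, in a trial of 10 participants. If the dosing line contains a text error, staff who follow it would under-label participants, and that cannot be repaired after the biopsies.

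The saliva rule raises a second, smaller question about the same denominator. A sample taken before the day's dose and one taken after it has mixed differ by one full dose. The rule accepts either, so the measured precursor depends partly on when the participant happened to sample.

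**Working it through.** **Inputs from the Methods:** 70% D2O; 0.8 ml per kg lean mass per dose; four doses on the loading day; one per maintenance day; target about 1%.

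**Assumptions, not in the documents:** body water W = 0.65–0.80 L per kg lean mass (central 0.73); body-water half-life 6–12 days; full mixing of each dose; labelling for 8 days after loading.

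**1. Loading day.**
- D2O given: 4 × 0.8 × 0.70 = 2.24 ml/kg.
- Enrichment = 2.24 / (1000 W): 2.24/650 = 0.34%; 2.24/730 = 0.31%; 2.24/800 = 0.28%.
- Treating the doses as pure D2O, 3.2/800 to 3.2/650 = 0.40–0.49%.
- For this load to give 1%, W would have to be 2.24/0.01 = 224 ml/kg, which is not plausible.
- The stated ~1% is therefore not reproduced from the load.
- To reach 1% on the loading day takes 6.5–8.0 ml/kg of D2O, or 2.9–3.6 times the stated load. That is four doses of about 2.3–2.9 ml/kg, or about 12–14 doses of 0.8 ml/kg.

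**2. Load plus maintenance.**
- One dose adds m = 0.8 × 0.70 / (1000 W) = 0.070–0.086 percentage points.
- With k = ln 2 / half-life, E(t+1) = E(t)·exp(−k) + m, starting from the post-load level.
- Central example (W = 0.73, half-life 8 days): exp(−k) = 0.917 and exp(−8k) = 0.5. So E(8) = 0.307 × 0.5 + 0.0767 × 0.5/0.083 = 0.62%. The time-average over the 8 days is 0.44%.

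| W (L/kg), half-life | End of day 8 | 8-day average | End of day 28 |
|---|---|---|---|
| 0.80, 6 d | 0.50% | 0.37% | 0.63% |
| 0.73, 8 d | 0.62% | 0.44% | 0.87% |
| 0.65, 12 d | 0.79% | 0.54% | 1.30% |

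- At a 12-day half-life, the end level first reaches 1% on day 14 (W = 0.65) to day 24 (W = 0.80).
- At 10 days and W = 0.70–0.75, it does so on days 22–29.
- At 6 days it never does: the plateau m/(1 − exp(−k)) is 0.64–0.79%.

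**3. Saliva timing.**
- One dose relative to the post-load level: 0.56/2.24 = 25%. Relative to the day-8 level: 11–14%, for half-lives of 12 to 6 days.
- If each of 8 samples is before or after the dose at random, half and half, the SD added to the mean is m × 0.5/√8. In the central example this is 0.0767 × 0.5/2.83 = 0.0136 points on a mean of 0.46%, or 2.9%. The range is 2.7–3.2%.
- If every sample is pre-dose in one period and post-dose in the other, the ratio of 8-day means is 1.165–1.201.

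**4. Cost of pre-dose sampling.**
- The simple mean of pre-dose samples divided by the true time-average is k·exp(−k)/(1 − exp(−k)): 0.943 at 6 days and 0.971 at 12 days, or 3–6% low.
- Adding the known dose increment to each pre-dose value and then using the trapezoid rule gives 1.0011 and 1.0003 of the true average.

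**The case against.** The strongest reply is that ~1% is attached to the whole schedule, not to the loading day. The sentence does read that way, and this stands. A reader might infer from the 0.3% figure that the schedule cannot reach 1%. The documents do not support that: the labelling duration is not visible, the half-life is assumed, and a course of 2–4 weeks at slow turnover can end near 1%. The trial is also a crossover. If dosing simply continued into a second 8-day period, the same model gives a day 8–16 average of 0.55–0.83% at 0.70–0.75 L/kg. The 8-day averages above therefore describe one course starting from zero enrichment.

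A second reply is that the nominal 1% enters no calculation. Measured saliva supplies the precursor, so the supplementation contrast is not biased by a wrong target. This also stands. The loss of precision cannot be sized without assay precision.

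A third reply is that saliva timing is largely handled by the advice to sample on waking. Participants who follow it will mostly sample before the dose. It remains advice, however, and the rule expressly permits a post-dose sample. Nothing in the documents suggests the systematic pattern behind the 17–20% shift.

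**Conclusion.** The stated doses do not deliver about 1% on the loading day (0.28–0.34%). They do not do so over the only duration in the readable text either: about 0.5–0.8% at day 8 and about 0.4–0.5% on average, given the assumed water turnover and 8 labelling days. The loading-day result rests only on the body-water assumption and is firm across any plausible range. The later figures are conditional on labelling duration and half-life. The consequence is less muscle label than the stated target implies, of unknown importance for precision.

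The saliva rule leaves an avoidable error in the primary-outcome denominator: about 3% SD on a participant's 8-day mean under random timing. The 17–20% shift between periods is an extreme upper bound that needs opposite timing throughout and full mixing. It is not an expected error.

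A reader might also infer that the dose is a misprint or that the treatment comparison is biased. Neither is shown. This is a low-severity clarification.

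**What to change.** 1. In the Methods sentence, check the loading-dose volume and count against the intended ~1%, and correct them if the text is in error. The loading line is the place to look first. Holding 1% once reached would take (1 − exp(−k)) × 1000 W × 0.01/0.70 = 0.52–1.25 ml/kg per day, which contains the stated 0.8, while the load is about a third of what reaches 1%. If the doses are as intended, replace ~1% with about 0.3% after loading and the expected average over the actual number of labelling days, and state that number.

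2. In saliva step 1, require the sample on waking, before food, drink or that day's D2O, and delete the 30-minutes-after option for D2O.

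Restating the enrichment costs only wording and a less favourable stated figure. Correcting the load would mean roughly three times the tracer on that day. Daily saliva is already collected, so the second change costs slightly less convenience for participants. The 3–6% shortfall of a simple pre-dose mean is similar in both conditions, and adding the known dose increment before time-weighting removes nearly all of it.
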